## 7. STATISTICAL CONSIDERATION

### 7.1. Hypotheses to be Tested

#### 7.1.1. Primary Endpoints:

The null hypothesis ( $H_0$ ) for the primary endpoint is that the difference in proportion of patients achieving 100% re-epithelialization by week 12 between the synthetic hybrid-scale fiber matrix group ( $\pi_1$ ) and the control group ( $\pi_2$ ) is less than or equal to the superiority margin of +0.10 based on a one-sided Farrington & Manning test. The alternative hypothesis ( $H_1$ ) is that the difference is less than the superiority margin of +0.10. These can be seen in the equations below:

$$H_0: \pi_1 - \pi_2 \geq +0.10$$

$$H_1: \pi_1 - \pi_2 < +0.10$$

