### **7.3. Sample Size Calculation**

Sample size calculations were performed using a Farrington & Manning test for superiority of the synthetic hybrid-scale fiber matrix group compared to the control group. Under assumptions of a closure rate of 80% for the synthetic hybrid-scale fiber matrix group, 40% for the control group, and a superiority margin of 10%, this results in a sample size of 20 per group (40 total) that provides a power of 0.8 and one-sided alpha of 0.05. After allowing for an assumed 20% lost to follow up, this results in a total sample size of 48 patients.

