## **7.6. Study Outcome**

### **7.6.1. Primary Endpoints**

100% re-epithelialization will be assessed every week for 12 weeks or until 100% re-epithelialization, whichever occurs first. Persistence of wound closure will be verified via confirmatory visit within 2 weeks after complete closure has been first determined.

For the primary endpoint of 100% re-epithelialization at week 12 a two-stage analysis will test first if the rate of 100% re-epithelialization is superior between groups using a chi squared and/or Farrington & Manning test. Superiority for synthetic hybrid-scale fiber matrix will be demonstrated if the lower bound of the 90% CI of the difference in proportions lies above the superiority margin of +10%.

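### Section 7.1.1 prints the alternative and both hypothesis equations backwards, and the 90% CI success rule in 7.6.1 names no interval method and sits beside a chi-squared option that cannot test the margin

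*Combined protocol and SAP*

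**What the plan says.** Section 7.1.1 makes four statements about the primary hypothesis, where π1 is the closure proportion on the matrix and π2 that on control:

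- Null, in words: the difference "is less than or equal to the superiority margin of +0.10 based on a one-sided Farrington & Manning test".
- Alternative, in words: it "is that the difference is less than the superiority margin of +0.10".
- Null, as an equation: "H_0: \pi_1 - \pi_2 \geq +0.10".
- Alternative, as an equation: "H_1: \pi_1 - \pi_2 < +0.10".

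Section 7.3 sizes the trial with a "Farrington & Manning test for superiority of the synthetic hybrid-scale fiber matrix group compared to the control group", at 80% vs 40% closure and a 10-point margin, for "power of 0.8 and one-sided alpha of 0.05".

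Section 7.6.1 announces an analysis in two stages. Its first stage asks whether the closure rate is "superior between groups using a chi squared and/or Farrington & Manning test"; no second stage follows. Success is declared if the "lower bound of the 90% CI of the difference in proportions lies above the superiority margin of +10" percentage points. No method for that interval is given.

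Section 7.8 imputes missing closure status 50 times, runs the one-sided Farrington-Manning test on each dataset and pools to a single p-value. It does not mention the confidence bound.

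**The concern.** **Direction.** The two sentences in 7.1.1 overlap: a difference below +0.10 satisfies both. Neither covers a difference above +0.10, which is what the trial sets out to show. The equations do cover the whole range, but they put the desired result in the null. A significant result under them would be evidence against the product. Section 7.8 calls for a one-sided Farrington-Manning test without restating its direction, so the reader has to go back to 7.1.1. Section 7.4 does not settle it either, because it labels the interim statistic and its promising zone as non-inferiority.

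**Decision rule.** The CI rule in 7.6.1 points the right way and keeps the margin. Different 90% intervals for a difference in proportions give different lower bounds at 20 to 24 per group, so the rule and the Farrington-Manning test can disagree in either direction. An ordinary chi-squared test has zero difference as its null and cannot address a 10-point margin. With neither the interval nor the deciding test fixed, the documents leave room to choose after the data are seen.

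**Working it through.** **1. Direction, side by side**

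| Place | What it implies for the alternative |
|---|---|
| 7.1.1, null sentence (≤ +0.10) | > +0.10 |
| 7.1.1, alternative sentence | < +0.10 |
| 7.1.1, null equation (≥ +0.10) | < +0.10 |
| 7.1.1, alternative equation | < +0.10 |
| 7.3, superiority, 80% vs 40% (difference +0.40) | > +0.10 |
| 7.6.1, lower bound above +10 points | > +0.10 |

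Three of the four statements in 7.1.1 are reversed. The error is in plain words as well as symbols, so damage to the symbols in PDF conversion is an unlikely explanation.

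**2. The plan's own figure**

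Section 7.3 gives 20 per group. In the intended direction the Farrington-Manning (FM) formula is

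n = [z0.95·√V0 + z0.80·√V1]² / (0.40 − 0.10)².

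- V0 uses the restricted estimates under a 0.10 difference, 0.657 and 0.557: 0.657×0.343 + 0.557×0.443 = 0.472.
- V1 = 0.8×0.2 + 0.4×0.6 = 0.40.
- n = (1.645×0.687 + 0.842×0.632)² / 0.09 = 30.7, so 31 per group.

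The stated 20 is not reproduced. That shortfall is a separate matter. Correcting the direction neither causes nor cures it. The figures below use 20 (evaluable) and 24 (randomized) per group.

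**3. The printed equations taken literally**

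The FM statistic is z = (p1 − p2 − 0.10)/SE, with SE from the restricted estimates. The printed equations would reject when z < −1.645. Exact binomial enumeration gives:

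| True rates, matrix vs control | 20 per group | 24 per group |
|---|---|---|
| 80% vs 40% | 0.0001 | 0.00004 |
| 40% vs 40% | 15.0% | 16.5% |
| 30% vs 50% | 60.4% | 67.4% |

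**4. The CI rule under three intervals**

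Success means a 90% lower bound above 0.10. The score bound is the one that matches the FM test.

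| | Score/FM | Wald | Newcombe |
|---|---|---|---|
| Error at 50% vs 40%, n = 20 | 4.7% | 7.4% | 4.1% |
| Error at 50% vs 40%, n = 24 | 5.1% | 6.7% | 4.3% |
| Maximum error, control 0–90%, n = 20 | 7.3% | 7.5% | 4.8% |
| Maximum error, control 0–90%, n = 24 | 5.6% | 6.8% | 5.1% |
| Success at 80% vs 40%, n = 20 | 65.0% | 70.8% | 61.4% |
| Success at 80% vs 40%, n = 24 | 72.9% | 75.6% | 70.3% |

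Disagreement, with its probability at 80% vs 40%:

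- 24 per group: score and Wald differ in 5 of 625 tables (2.7%). The three are not unanimous in 9 of 625 (5.2%).
- 20 per group: 6 of 441 (5.8%) and 10 of 441 (9.4%).

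**5. Two tables that show it**

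Both have an observed difference of 8/24 = 0.333.

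*17/24 vs 9/24*
- FM: restricted estimates 0.594 and 0.494, SE 0.143, z = 0.2333/0.143 = 1.63, p = 0.051. The score bound is 9.8%, which fails.
- Wald: SE = √(0.708×0.292/24 + 0.375×0.625/24) = 0.1356. The bound is 0.333 − 1.645×0.1356 = 11.0%, which passes.
- Newcombe: the Wilson limits are 0.541 (lower, matrix) and 0.542 (upper, control). The bound is 0.333 − √(0.167² + 0.167²) = 9.7%, which fails.

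*18/24 vs 10/24*
- FM: p = 0.049. The score bound is 10.1%, which passes.
- Wald: 11.3%, which passes.
- Newcombe: 9.9%, which fails.

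The FM test can therefore fail where a Wald rule passes, and pass where a Newcombe rule fails.

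**6. Chi-squared (assumed reading only)**

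No section says a significant chi-squared result alone is success. If it were, the uncorrected test would favour the matrix at 50% vs 40% with probability 8.3% / 11.6% (two-sided 0.05) or 13.9% / 18.3% (one-sided 0.05) at 20 / 24 per group. This only illustrates that the test ignores the margin.

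**The case against.** **The direction error changes no operative decision.** The null sentence is right, 7.3 plans for superiority, and 7.6.1 states one success rule in the right direction. The literal-reading probabilities require the equations to override all three, and no section describes rejecting at z < −1.645. This is fair. Those figures show what the misprint says and do not forecast the trial's conduct. It does not remove the need to correct the plan's only formal statement of the primary hypothesis, which is reversed in three of its four parts.

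**The interval can be inferred.** FM is named in 7.1.1, 7.3, 7.4 and 7.8 and immediately before the CI rule, while Wald and Newcombe appear nowhere. The matching score bound is the natural reading, but it is not written down. Section 7.8 mentions a formal analysis plan still to come, which might settle the interval. That text defers only the imputation variables.

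**The numerical effect is small.** This stands. The contrast of 4.7% with 7.4% belongs to one point, 50% vs 40% at 20 per group. The maximum errors there are nearly equal for score and Wald (7.3% and 7.5%). Because 7.8 imputes missing outcomes, 24 per group is closer to the planned analysis, and the gap at 50% vs 40% is narrower there (5.1% vs 6.7%). The interval gap therefore deserves a lower grade than the direction error.

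**Conclusion.** The concern holds.

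- **Direction: wrong as written and must be corrected.** The intended alternative, a difference greater than +0.10, is clear from 7.3, 7.6.1 and the null sentence. This conclusion rests on the text alone and needs no assumption.
- **Decision rule: should be completed.** The interval method is unnamed, the role of chi-squared is open, the second stage is missing, and 7.8 gives no way to pool the bound. At 80% vs 40%, the three common intervals are not unanimous with probability 5.2% at 24 per group and 9.4% at 20. The 90% level itself is sound, since its lower bound corresponds to one-sided 0.05.

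The figures assume fixed, equal groups and complete outcomes. They leave out the sample-size re-estimation in 7.4 and the imputation in 7.8. The chi-squared-only error rates are not part of this conclusion.

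**What to change.** 1. In 7.1.1 write H0: π1 − π2 ≤ +0.10 and H1: π1 − π2 > +0.10, and change the alternative sentence to say greater than.
2. In 7.6.1 name one test and one interval as the sole primary decision. The choice consistent with 7.1.1, 7.3 and 7.8 is the one-sided 0.05 Farrington-Manning test with its score-based 90% lower bound above +0.10. Another pre-named interval, such as Newcombe, is defensible if the Farrington-Manning references are changed to match.
3. Remove the and/or. Keep chi-squared only as a supportive test of zero difference, and state its level, sidedness and continuity correction.
4. Define the second stage or drop the reference to two stages.
5. In 7.8 say how the 90% bound is combined across the 50 imputed datasets.

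The cost is a few lines of text, with no change to the design. At 80% vs 40%, choosing the score bound gives up 5.8 points of success probability against Wald at 20 per group (65.0% vs 70.8%) and 2.7 points at 24 (72.9% vs 75.6%). It gains 3.6 and 2.6 points against Newcombe (61.4% and 70.3%).

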### 7.2. Analysis Populations

#### Intention to Treat Population (ITT)

The ITT population will consist of all enrolled patients. Patients are considered enrolled after meeting the criteria specified in Section 4. Patients in the ITT

population will be evaluated based on the randomized treatment group.

#### Modified Intention to Treat Population (mITT)

The mITT population will consist of ITT patients who have at least one product application. This will serve as the primary analysis population for study efficacy. Patients in the mITT population will be evaluated based on the randomized treatment group.

#### Per Protocol (PP)

The PP will include all ITT patients who additionally meet all study eligibility criteria, have available study data for the primary study endpoint and do not have a major protocol violation that affects primary effectiveness. Patients in the PP population will be evaluated based upon the treatment that they receive.

### **7.3. Sample Size Calculation**

Sample size calculations were performed using a Farrington & Manning test for superiority of the synthetic hybrid-scale fiber matrix group compared to the control group. Under assumptions of a closure rate of 80% for the synthetic hybrid-scale fiber matrix group, 40% for the control group, and a superiority margin of 10%, this results in a sample size of 20 per group (40 total) that provides a power of 0.8 and one-sided alpha of 0.05. After allowing for an assumed 20% lost to follow up, this results in a total sample size of 48 patients.

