## **3. STUDY DESIGN**

**Condition:** Diabetic Foot Ulcer (DFU)

**Aim:** Comparatively assess wound closure in diabetic foot ulcers treated with synthetic hybrid-scale fiber matrix or standard of care in a randomized, controlled clinical trial.

**Number of Patients:** 48 subjects (24 subjects in the experimental arm and 24 subjects in the control arm)

**Number of Sites:** 2

**Study Type:** Interventional

**Study Design:** Allocation: Randomized (1:1 ratio)  
Endpoint Classification: Efficacy  
Intervention Model: Direct assignment

Masking: Single Blind (Subject)

Primary Purpose: Treatment

**Control Group:** Treatment with Standard of Care (weekly)

**Test Group:** Treatment with Synthetic Hybrid-Scale Fiber Matrix (weekly or as needed based on the clinician discretion and ongoing wound assessment)

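### Section 7.3 claims 80% power, but 20 per group gives about 65% for the margin test it names, and 48 patients do not cover the assumed 20% loss

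*Combined protocol and SAP*

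**What the plan says.** Section 7.3 gives every input to the calculation. The method: "Sample size calculations were performed using a Farrington & Manning test for superiority of the synthetic hybrid-scale fiber matrix group compared to the control group". The assumed rates: "closure rate of 80% for the synthetic hybrid-scale fiber matrix group, 40% for the control group". The margin is 10 percentage points. The result: "this results in a sample size of 20 per group (40 total) that provides a power of 0.8 and one-sided alpha of 0.05". The loss allowance: "After allowing for an assumed 20% lost to follow up, this results in a total sample size of 48 patients". Section 3 carries the total forward as "48 subjects (24 subjects in the experimental arm and 24 subjects in the control arm"), allocated 1:1.

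Two other sections confirm the margin and the error rate. Section 7.1.1 refers to a "superiority margin of +0.10 based on a one-sided Farrington & Manning test". Section 7.6.1 declares success if the "lower bound of the 90% CI of the difference in proportions lies above the superiority margin of +10" percent, and the lower limit of a two-sided 90% interval corresponds to a one-sided 0.05 test. The inequalities printed in 7.1.1 run opposite to this success rule. The direction used here is that of 7.6.1, which is also the direction implied by the sizing in 7.3.

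**The concern.** The assumed difference is 40 points, but the test must clear 10 of them, so the distance that drives power is only 30 points. Twenty patients per group is small for that distance at one-sided 0.05. The step from 40 to 48 patients also looks like multiplication by 1.20 rather than division by 0.80.

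The stated power is what the sponsor, the IRB and later readers use to judge a negative result. If the true power is well below 80%, a miss is quite likely even when the device performs exactly as assumed. It could then be taken as evidence that the device does not beat standard care by 10 points. Section 2.2 says the data are meant to inform payor coverage decisions, so that reading would have consequences.

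**Working it through.** **Inputs (section 7.3; allocation from section 3).** p1 = 0.80, p2 = 0.40, margin d = 0.10, one-sided α = 0.05 (z = 1.645), target power 0.80 (z = 0.842), 1:1 allocation. The distance from the margin is 0.40 − 0.10 = 0.30.

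**Variances.**
- Under the alternative: 0.80×0.20 + 0.40×0.60 = 0.16 + 0.24 = 0.40, so s1 = 0.6325.
- Under the null (Farrington-Manning): the maximum likelihood rates restricted to a difference of 0.10 are 0.657 and 0.557. The variance is 0.657×0.343 + 0.557×0.443 = 0.472, so s0 = 0.687.

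**Trying to reproduce 20 per group.**
- Farrington-Manning: n = [(1.645×0.687 + 0.842×0.6325)/0.30]² = (1.663/0.30)² = 30.7, so 31 per group.
- Unpooled variance: n = (1.645 + 0.842)² × 0.40/0.30² = 27.5, so 28 per group.

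Neither gives 20. A one-sided α of 0.10 (z = 1.282) in the unpooled formula gives (1.282 + 0.842)² × 0.40/0.09 ≈ 20.03, with power 79.9% at 20 per group. The figure may therefore have been computed at twice the stated α. That is a conjecture, since the plan does not say how 20 arose, and the Farrington-Manning formula at α = 0.10 gives 23.

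**Power at 20 per group.**
- Farrington-Manning: Φ[(0.30×√20 − 1.645×0.687)/0.6325] = Φ[(1.342 − 1.130)/0.6325] = Φ(0.334) = 63.1%.
- Unpooled: Φ(1.342/0.6325 − 1.645) = Φ(0.476) = 68.3%.
- Exact: summing the binomial probabilities of all outcomes whose Farrington-Manning statistic reaches 1.645 gives 65.0%.

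| Evaluable per group | FM asymptotic | FM exact | Unpooled |
|---|---|---|---|
| 19 (48 less 20%) | 61.0% | 66.3% | 66.4% |
| 20 (section 7.3) | 63.1% | 65.0% | 68.3% |
| 24 (no loss) | 70.4% | 72.9% | 75.1% |
| 28 | 76.5% | 79.4% | 80.7% |
| 31 | 80.3% | 80.5% | 84.0% |

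The exact column need not rise steadily, because the test is discrete; that is why 19 per group shows slightly more than 20. Other versions of the margin test at 20 per group give 62.5% (pooled variance), 70.8% (Wald, exact enumeration) and 58.0% (Wald with continuity correction).

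**What 20 per group would need for 80% power.** With the matrix at 80%, control closure would have to be about 33% (Farrington-Manning) or 35% (unpooled) instead of 40%.

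**What 24 per group with no loss can detect.** With the matrix at 80% and control at 36%, the distance from the margin is 0.34. The restricted rates are 0.636 and 0.536, so s0 = 0.693, and s1 = √(0.16 + 0.2304) = 0.625. Power is Φ[(0.34×√24 − 1.645×0.693)/0.625] = Φ(0.84) = 80%. The detectable difference is about 44 points, not 40.

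**Loss.** 40 × 1.20 = 48, but 48 × 0.80 = 38.4, which is below 40. Retaining 40 needs 40/0.80 = 50. Forty-eight covers a loss of 1 − 40/48 = 16.7%.

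**Sample size re-estimation (section 7.4).** The printed rule was enumerated with 12 per group at the interim, no loss, the sponsor always accepting the increase, and the unadjusted Farrington-Manning test at the end. Under 80% vs 40%, the promising zone is entered 23% of the time. Overall power is 75.1% if the cap of 70 means total patients and 76.5% if it means per group.

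**The case against.** **More patients than 40 may count.** The trial enrolls 48, the primary population is the modified intention-to-treat set, section 7.8 imputes missing closure, and section 7.4 works from a planned final sample of 48. With full data the chance of a miss is 25% to 30%, nearer one in four. This stands: one in three applies only if about 20% of outcomes are lost and imputation recovers little. But that 20% loss is the plan's own assumption, and the best case is still short of 80%.

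**Sample size re-estimation could restore power.** An increase is triggered only when conditional power lies between 42% and 80%, and the sponsor may decline it. Accepted every time and with no loss, it still leaves power at about 75% to 77%. It cannot make the fixed-design statement in 7.3 correct.

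**Section 7.6.1 also allows a chi-squared test.** Without a margin, 20 per group has 84.8% power one-sided and 75.2% two-sided (normal approximation). The conclusion must therefore be limited to the 10-point margin test at one-sided 0.05. That is the test 7.3 says it sized, and the interval rule in 7.6.1 keeps the margin.

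**The loss slip is small.** This is fair. It amounts to two patients and about 2 points of power by the asymptotic formula.

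**Conclusion.** The power statement in section 7.3 is wrong. For the stated rates, margin and one-sided 0.05 level, 20 per group gives about 65% power (63% to 68% by the three main methods, 58% to 71% over every variant of the margin test tried). The overstatement is 12 to 17 points by the main methods. The number needed for 80% is 31 evaluable per group by Farrington-Manning, or 28 unpooled. No version of the margin test at the stated level reaches 80% with 20 or with 24 per group.

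The chance of missing the endpoint when the sponsor's assumptions are true is about one in three at 19 to 20 evaluable per group, and 25% to 30% if nobody is lost. The plan implies one in five. The loss arithmetic is also wrong, but is a minor matter beside this.

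The result assumes 1:1 allocation and independent binomial outcomes. All other inputs are printed in the plan. The Type I error is not affected by this mistake.

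**What to change.** Rewrite section 7.3 to say that:

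- at 80% vs 40% closure, a 10-point margin and one-sided α of 0.05, 20 evaluable per group gives about 65% power by the Farrington-Manning test, and 24 per group with no loss gives about 73%;
- 80% power at these inputs would need about 31 evaluable per group (62 in total; 62/0.80 = 77.5, so 78 enrolled with 20% loss);
- for loss, either 50 patients are needed to retain 40, or 48 patients retain about 38;
- if 48 is kept, the effect it can detect with 80% power. With no loss and the matrix at 80%, this corresponds to control closure of about 36% (a 44-point difference); it would be larger after 20% loss.

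Name the software, variance method and α used, so that the figure can be reproduced.

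The cost is a rewording of one section and a less favourable power statement. Enrollment, the test and the success rule can stay as they are. Whether to enroll more patients is the sponsor's decision, to be made with the correct figure.

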### **7.4. Interim and Final Analyses**

An unblinded interim assessment for sample size re-estimation (SSR) will be performed on the primary endpoint of the study by an independent statistician. The analysis will be conducted when 50% of the mITT population (24 patients) have been enrolled and completed the primary endpoint evaluation. The analysis described below will be performed on the mITT population.

The purposes of the interim analysis are (1) to calculate the power for superiority, conditioned on the interim-observed difference between treatments with respect to 100% re-epithelialization rates and on the superiority margin of 10%, and (2) determine if the sample size needs to be increased in order to maintain the desired conditional power of 80%.

The conditional power will be calculated under the assumption that the interim observed estimate of the treatment difference is the true treatment difference. It will be calculated using the following formula as discussed in Lan and Wittes (1988) where:

$$1 - \Phi\left[\frac{Z_{1-\alpha} - B_\tau / \tau}{\sqrt{1-\tau}}\right]$$

$Z_{1-\alpha}$  is the  $(1-\alpha) \times 100\%$  percentile of the standard normal distribution (i.e., the critical value used to assess superiority at the final analysis at overall one-sided significance level  $\alpha$ ).

$\tau$  is the information fraction (= proportion of patients in the first interim analysis =  $r/M$  where  $r$  is the number of patients per group in the interim analysis and  $M$  is the planned number of patients per group for the final analysis); if the interim sample sizes per group are not equal due to randomness, the harmonic mean of the sample size will be used.

$B_\tau = Z_\tau \sqrt{\tau}$  where  $Z_\tau$  = the Farrington-Manning non-inferiority test statistic calculated on the interim observed data.  $\Phi$  is the cumulative distribution function of the standard normal distribution.

Following the “promising zone” algorithm in Mehta and Pocock (2011), if the conditional power based on the planned final sample size of 48 patients is  $<42\%$  or  $>80\%$  at the interim stage, the study will continue as is (there will be no stoppage of the study for futility nor will there be a sample size increase). If the conditional power is between 42-80% (the promising zone), the sample size may then be re-estimated using the method described by Wang et al (2002) in order to maintain 80% conditional power without increasing the Type I error (probability of a false positive result) of the study. Specifically, the total revised sample size per group,  $M'$  required to achieve a conditional power of 80% to assess superiority at the final analysis using a superiority margin of 10% is found by solving the following equation for  $M'$ :

$$Z_{0.20} \sqrt{1 - \frac{r}{M'}} + Z_\tau \sqrt{\frac{M'}{r}} - Z_{1-\alpha} = 0$$

where  $Z_{0.20}$  is the 20th percentile of the standard normal distribution (corresponding to the desired 80% conditional power) and where all other variables in this equation are defined above.  $M'$  will not exceed 70 patients for the DFU arm. This formula assumes the interim observed effect size between treatments is the true effect size between treatments.

Results of the interim assessment will be presented by the independent statistician to the Sponsor group. The report to the Sponsor will state if additional sample is required to achieve a conditional power of 80%, and if so, how many additional patients. If additional sample size is required, the Sponsor will make a decision to either enroll the additional patients or not enroll and accept that the primary

endpoint may be under-powered. The independent statistician's report containing the results that led to the independent statistician's recommendation will be kept confidential within the select Sponsor group.

The following decision rules outline the possible outcomes of the interim analysis:

1. If the test for  $CPni < 0.42$  or  $\geq 0.8$ , then there is no increase in the sample size and the trial will be completed on a minimum of 48 enrolled patients, as scheduled.

If the test for conditional power is  $0.42 \leq CPni < 0.8$ , then the sample size will be increased by just the right amount such that  $CPni$  is increased to 0.8, under a cap of 70 patients. The range  $0.42 \leq CPni < 0.8$  is called the promising zone for non-inferiority. Specifically, if  $CPni$  is in its promising zone, this decision rule increases the sample size by the smallest of 70 patients or the number needed to boost  $CPni$  to 0.8.

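### Section 7.4 divides completers at the interim by enrolled patients at the end, so conditional power is overstated: a nominal 80% is about 74% (range 72–76%)

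*Combined protocol and SAP*

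**What the plan says.** **Interim trigger and numerator (section 7.4).** "The analysis will be conducted when 50% of the mITT population (24 patients) have been enrolled and completed the primary endpoint evaluation". With 1:1 allocation (section 3) that is r = 12 per group. The interim test statistic is computed on the data observed at that point.

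**Denominator (section 7.4).** The information fraction is τ = r/M, with M the number per group planned for the final analysis. The decision is taken "if the conditional power based on the planned final sample size of 48 patients" lies below, inside or above the 42–80% zone. So M = 24 per group. The first decision rule in the same section describes these 48 as enrolled patients.

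**Where 48 comes from (section 7.3).** The calculation is for "a closure rate of 80% for the synthetic hybrid-scale fiber matrix group, 40% for the control group, and a superiority margin of 10" percent; "this results in a sample size of 20 per group (40 total") evaluable patients. Then: "After allowing for an assumed 20% lost to follow up, this results in a total sample size of 48 patients".

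**Lost patients.** Section 7.2 keeps anyone with at least one application in the mITT population. Section 7.8 multiply imputes missing closure status. Section 7.4 does not say whether r or M counts imputed patients, and does not say whether the revised size M′ is inflated for loss.

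**The concern.** The numerator of τ counts patients whose endpoint is known. The denominator counts patients who will be enrolled, a number that the plan itself expects to shrink. τ is then too small, and the formula credits the second stage with information that will not arrive. The equation for M′ has the same gap: it returns the number per group needed with full information, and the plan uses it as an enrolment figure.

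Conditional power is the statistic on which the re-estimation rule turns. If it is overstated, a trial that belongs in the promising zone can be classed as favourable and left at 48. A trial below the entry threshold can be admitted to the zone. A trial that is enlarged still falls short of the stated 80%. The Sponsor receives a report framed around reaching 80% and decides on it.

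**Working it through.** **Inputs.** One-sided α = 0.05, so Z₁₋α = 1.645 (7.3). r = 12 per group (7.4, 1:1). M = 24 per group as written (7.4). 20 evaluable per group and 20% loss (7.3).

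**The plan's own figures.** 40 × 1.2 = 48, which reproduces (40/0.80 would be 50), and τ = 12/24 = 0.50. The 20 per group itself does not reproduce: a Farrington–Manning calculation with the stated inputs gives 31 per group. That is a separate matter, because conditional power uses only Z, r, M and α.

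**Evaluable patients per group at the end, three readings of the loss.**
- Section 7.3's own number: 20, τ = 12/20 = 0.60.
- 20% of all 48 lost: 48 × 0.80/2 = 19.2, τ = 0.625.
- Loss only among patients after the interim: 12 + 0.80 × 12 = 21.6, τ = 0.556.

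**Formula (7.4).** Since B_τ = Z_τ√τ, CP = 1 − Φ[(1.645 − Z_τ/√τ)/√(1 − τ)].

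**Upper boundary.** Nominal CP = 80% at τ = 0.50 needs Z_τ = 1.584: (1.645 − 1.584/0.7071)/0.7071 = −0.842, CP = 0.80. The same Z_τ at τ = 0.60: (1.645 − 1.584/0.7746)/0.6325 = −0.632, CP = 0.736.

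| Nominal CP (M = 24) | Z_τ | M = 21.6 | M = 20 | M = 19.2 |
|---|---|---|---|---|
| 80% | 1.584 | 76.4% | 73.6% | 72.1% |
| 70% | 1.425 | 65.6% | 62.1% | 60.2% |
| 50% | 1.163 | 45.0% | 41.0% | 38.8% |
| 42% | 1.062 | 37.1% | 33.3% | 31.1% |

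**Actual interim tables.** Z_τ is the Farrington–Manning statistic with margin 0.10. For 10/12 vs 5/12 the restricted estimates are 0.684 and 0.584, so Z_τ = (0.4167 − 0.10)/√[(0.684 × 0.316 + 0.584 × 0.416)/12] = 1.619.

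| Closures | Z_τ | M = 24 | M = 21.6 | M = 20 | M = 19.2 |
|---|---|---|---|---|---|
| 10/12 vs 5/12 | 1.619 | 81.9% | 78.6% | 75.9% | 74.5% |
| 9/12 vs 4/12 | 1.565 | 79.0% | 75.3% | 72.4% | 70.8% |
| 9/12 vs 5/12 | 1.167 | 50.3% | 45.3% | 41.4% | 39.2% |

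The first row (83% vs 42%, close to the design's 80% vs 40%) moves from no increase into the promising zone under every reading. The last row drops below the 42% entry with 19.2 or 20 per group, but not with 21.6.

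**Revised size.** The plan's equation is −0.842√(1 − 12/M′) + Z_τ√(M′/12) − 1.645 = 0. For Z_τ = 1.363 (11/12 vs 7/12) it gives M′ = 35.0 per group. If 35 are enrolled, 35 × 0.80 = 28 evaluable gives CP = 71.8%, and 35/1.2 = 29.2 gives 73.4%. Across the zone, where the cap does not bind, the results are 71.8–72.1% and 73.4–73.6%. If only post-interim patients are lost they are 73.6–76.4%.

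**Does imputation restore the loss?** For 9/12 vs 4/12, the second stage was simulated with missing outcomes multiply imputed and combined by Rubin's rules. The chance of final success was 80.7% with nothing missing, and 73.3% and 74.0% with 4 and 5 post-interim patients per arm missing.

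**The case against.** **The interim may already be like for like.** Section 7.4 speaks of half of the mITT population, and lost patients stay in that population and are imputed. If the 24 include lost patients with imputed status, both looks shrink alike (9.6/19.2 = 0.50) and there is no overstatement. This is the strongest objection, and the documents do not exclude it outright. But the trigger is "when 50% of the mITT population (24 patients) have been enrolled and completed the primary endpoint evaluation", and the statistic is taken from observed data; both favour completers. If the other reading is intended, the plan needs to say so.

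**The shortfall is modest beside the interim noise.** This is true: one more control closure moves nominal conditional power from 79% (9/12 vs 4/12) to 50% (9/12 vs 5/12). The Sponsor may also decline an increase, there is no futility stop, and the final test is unchanged. So the matter concerns power planning. The mismatch is nevertheless a systematic error in one direction, and it can be removed before any data are seen.

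**A reader might infer type I error inflation.** Since a nominal 42% is really 31–33%, one could suppose that increases are allowed where an unadjusted final test is not protected. Pairing 19.2 evaluable per group with a cap of 35 per group would put the protected region above about 38%. But 35 is an enrolment figure (and assumes that 70 is a total), so that pairing repeats the same mismatch. With an evaluable cap of 28 the bound is about 42%. Some interim values admitted by the plan do fall below that bound, yet integrating the rule as written with 20% loss (normal approximation) gives an overall one-sided error of 0.0495 with a cap of 35 per group and 0.0492 with 70 per group. Both are under 0.05.

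**Conclusion.** The point holds on the plain wording of section 7.4, read with section 7.3. τ should be 0.60 rather than 0.50. Conditional power at a nominal 80% is overstated by about 6 points (4 to 8 across loss assumptions), and at the nominal 42% threshold by about 9 points (5 to 11). A revised size used as an enrolment number reaches about 72–73% where the cap does not bind, or somewhat more if loss occurs only after the interim. The misclassification at the upper boundary does not depend on which loss assumption is used; at the lower boundary it needs 19.2 to 20 evaluable per group.

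This rests on r counting completers only, on the plan's loss assumption being about right, and on imputation from age, gender and covariates not yet named adding little information. The figure of 72% should not be quoted alone: it is the low end of the range, while section 7.3's own 20 per group gives 74%. The consequence is misstated conditional power and wrong sample-size decisions. The documents do not support a claim that the type I error is breached.

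**What to change.** In section 7.4, before the interim:

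1. Define r and M both as patients per group with an observed primary endpoint, with M = 20 as in section 7.3 (and following 7.3 if that number is revised).
2. Solve M′ as evaluable patients per group, convert it to enrolment with the plan's loss allowance, and then apply the existing cap. State the conversion: section 7.3 multiplies by 1.2, while dividing by 0.80 is what 20% loss strictly requires. State also whether the cap of 70 is a total or per group.
3. Apply the 42–80% zone to conditional power on this scale, and report the conditional power actually reached where the cap binds.

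Example: 10/12 vs 5/12 gives 75.9% with M = 20, inside the zone. The equation gives M′ = 22.6 evaluable per group; 22.6 × 1.2 = 27.1, so 28 enrolled per group instead of 24.

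The cost is a few sentences. Reported conditional powers become less favourable, and a re-estimated enrolment may be larger, within the existing cap. If the authors intend r to include lost and imputed patients, one sentence saying so removes the mismatch in τ, but the plan must still state whether M′ is inflated for loss.
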